5.0 STUDY PROCEDURES

5.1 Table 5: Time and Events Table

PROCEDURES/ASSESSMENTS	Baseline/screening ¹	Induction (1 cycle = 28 days) ± 3 days				Consolidation ⁷ (1 cycle = 28 days) (Optional ¹²) ± 3 days				Maintenance ⁷ (1 cycle = 21 days) ± 3 days		Off Treatment ¹⁰	Follow-up ¹¹
		5	6	7	8	C1D1 +Odd cycles	C2D1 +Even cycles						
Weeks ¹³		1	2	3	4								
Informed consent	X												
H&P and vital signs	X	X				X				X	X	X	X
Review of eligibility	X												
Performance status	X									X ⁹		X	X
Toxicity (include DLT) evaluation	X	X	X	X	X	X	X	X	X	X	X		
Scans ²	X ²				X ²				X ²	X ²			X
CBC and serum chemistries ³	X	X	X	X	X	X	X	X	X	X	X		
Serum amylase ⁴	X	X	X	X	X	X	X	X	X	X	X		
Pregnancy test	X												
TMA	X ⁵												
Serum EBV viral load	X	X				X				X	X		
Hepatitis B ⁹	X												
Peripheral Blood Banking ⁶	X	X ⁶								X ⁶	X ⁶		
Brentuximab vedotin ⁷		X	X	X		X	X	X		X	X		
Rituximab ⁸		X	X	X	X	X	X	X	X		X		

¹ All screening procedures should be completed within 28 days of registration

² Tumor assessment will be by means of PET/CT at screening, after induction (after fourth dose of induction rituximab and prior to starting consolidation) and after consolidation if applicable (after fourth dose of consolidation rituximab and prior to starting maintenance; patients with a CR after induction do not need to repeat a scan after consolidation). NOTE: Although PET/CT is preferred, patients may be assessed by CT alone at any time point. During maintenance, patients will have CT with contrast every 12 weeks (4 cycles), within 7 days prior to Day 1 of Cycle 1, 5, 9 etc... During the Maintenance phase, the treating physician may assess with CT or PET/CT at his/her discretion. In addition, an End of

Treatment scan will be performed 3-4 weeks after the last dose of study treatment.

³ CBC and Chemistry panels must be resulted prior to dosing to assess the need for dose delays or modifications.

⁴ Serum amylase levels may be drawn up to 72 hours prior to the dosing of brentuximab vedotin. If amylase level is elevated, lipase must also be drawn. See Section 4.3 regarding dose modifications for hyperamylasemia (with or without pancreatitis).

⁵ Procurement of tissue and completion of TMA may be done prior to or upon enrollment, but are not required for registration/eligibility purposes.

⁶Phase II patients only: One red top tube and one green top tube will be drawn at baseline OR day 1 of induction, and day 1 of the first 3 maintenance cycles. Blood products will be frozen and stored in the Pathology Core Facility for future, unspecified use.

⁷ Brentuximab vedotin will be given intravenously over approximately 30 minutes at the specified time points. The dose will be 1.2mg/kg during induction and optional consolidation (see section 4.1) and 1.8mg/kg during maintenance. Lab values for CBC and Chemistry panels must be resulted prior to dosing to assess for dose delays or modifications.

Consolidation treatment should start 7-21 days after the fourth induction dose of rituximab. Maintenance treatment should start 7-21 days after the fourth consolidation dose of rituximab.

⁸ Rituximab will be given intravenously at a dose of 375mg/m² at the specified time points. Rituximab should be given immediately before brentuximab vedotin on days when both drugs are administered. See section 4.1 for more details. Lab values for CBC and Chemistry panels must be resulted prior to dosing to assess for dose delays or modifications.⁹ Hepatitis testing at screening will include HepBsAg and HepBcAb within 4 months prior to registration. ¹⁰ The End of Treatment visit should take place 21-28 days after the patient's last dose of study drug.

¹¹ Patients will be followed every three months for one year following discontinuation of study treatment, then every six months for a total of three years following discontinuation of study treatment, or until death, whichever comes first.

¹² Consolidation treatment is optional for patients who achieve response (PR or CR; see section 4.1.3 regarding SD) after induction. In addition, any patients achieving CR to induction, in whom avoidance of Maintenance therapy is sought, can receive consolidation as their final planned therapy.

¹³ Treatment and assessments will take place on Day 1 of each Week

6.0 ASSESSMENT OF ENDPOINTS

6.1 Toxicity Definitions

6.1.1 **Evaluable for toxicity.**

All patients will be evaluable for toxicity from the time of their first treatment with study drug. This includes the primary endpoint of safety and the secondary endpoint of toxicity.

6.1.2 **Safety/tolerability**

Analyses will be performed for all patients having received at least one dose of study drug. The study will use the CTCAE version 4.03 for reporting of non-hematologic adverse events (<http://ctep.cancer.gov/reporting/ctc.html>) and modified criteria for hematologic adverse events.

6.2 Efficacy Definitions

6.2.1 Response and progression will be evaluated in Phases I and II using 2007 Revised Response Criteria for Malignant Lymphoma (modified).

6.2.1.1 Evaluable for objective response.

Only those patients who have measurable disease (at least 1cm) present at baseline, have received *at least three doses of brentuximab vedotin*, and have had their disease re-evaluated will be considered evaluable for response. These patients will have their response classified according to the definitions stated below. (Note: Patients who exhibit objective disease progression prior to the end of cycle 1 will also be considered evaluable.)

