4.9 Patient Replacement

During Phase I, all three patients enrolled at the starting dose level must be observed for one cycle (21 days), at which point the study will be temporarily suspended for toxicity evaluation, before which it may either be reopened for an additional cohort (at either the same dose or a lower dose), or proceed to Phase II (as outlined in sections 4.1.2 and 4.1.3). Any DLT noted at any point after treatment begins (up till the end of the DLT evaluation period) shall count toward the total number of DLT, and patients are not replaced. An exception will be made for those patients who are enrolled but, for whatever reason, never receive treatment; such patients should be replaced. If a patient is withdrawn from the study within 21 days of starting therapy, for whatever reason, but without experiencing a DLT prior to withdrawal, an additional patient may be added to that dose level. Patients missing more than three weeks' worth of doses due to toxicity will not be replaced since these patients will be considered to have experienced a dose limiting toxicity.

During Phase II, any patient who is enrolled but not treated on the study, or who completes fewer than two total cycles of therapy and is withdrawn for any reason except POD or toxicity, shall be replaced.

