6.2.1.2 Evaluable for Survival

All patients who have had at least one dose of study treatment will be evaluable for PFS and OS.

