6.2.2.2 Evaluation of Best Overall Response
 The best overall response is the best response recorded from the start of the treatment until disease progression/recurrence (taking as reference for progressive disease the smallest measurements recorded since the treatment started). The patient's best response assignment will depend on the achievement of both measurement and confirmation criteria.

Target Lesions	Non-Target Lesions	New Lesions	Overall Response	Best Response for this Category Also Requires:
CR	CR	No	CR	≥ 4 wks. confirmation
CR	Non-CR/Non-PD	No	PR	≥ 4 wks. confirmation
PR	Non-PD	No	PR	
SD	Non-PD	No	SD	documented at least once ≥ 4 wks. from baseline
PD	Any	Yes or No	PD	no prior SD, PR or CR
Any	PD*	Yes or No	PD	
Any	Any	Yes	PD	

* In exceptional circumstances, unequivocal progression in non-target lesions may be accepted as disease progression.

Note: Patients with a global deterioration of health status requiring discontinuation of treatment without objective evidence of disease progression at that time should be reported as "*symptomatic deterioration*". Every effort should be made to document the objective progression even after discontinuation of treatment.

Note: If subjects respond to treatment and are able to have their disease resected, the patient's response will be assessed prior to the surgery.

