10.1.2 Phase II

Our null hypothesis is that the combination of rituximab and brentuximab vedotin will yield no difference in the rate of ORR as compared to that observed with historical treatments. The historical ORR for both PTLD and EBV-related

lymphoma of the elderly, when treated with rituximab (with or without chemotherapy is estimated at approximately 50% [1, 2]. Therefore, the optimal two-stage design to test the null hypothesis that $P=0.50$ versus the alternative that $P>=0.70$ (the hypothesized ORR to rituximab plus brentuximab vedotin) has an expected sample size of 24. Under these conditions, if the combination is actually not significantly more efficacious, there is a <0.05 probability (also known as the alpha value) of concluding that it is. If the combination is actually significantly more efficacious, there is a <0.20 probability (also known as the beta value) of concluding that it is not. Early futility may be declared, such that if eight or fewer responses are observed among the first 15 patients enrolled, the trial will be stopped and considered no more efficacious than therapy with rituximab alone.

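### The response set in 6.2.1.1 can leave treated early failures out of the Phase II ORR, and 10.1.2, 7.5 and 4.9 do not say how to count them

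*Combined protocol and SAP*

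**What the plan says.** Section 6.2.1.1 sets three conditions for the response analysis: measurable baseline disease, at least three brentuximab vedotin doses, and a repeat disease assessment ("and have had their disease re-evaluated will be considered evaluable for response"). A note adds one exception: "Patients who exhibit objective disease progression prior to the end of cycle 1 will also be considered evaluable".

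The other main endpoints carry no such condition. Section 6.2.1.2 has "All patients who have had at least one dose of study treatment will be evaluable for PFS and OS", and 6.1.2 has "Analyses will be performed for all patients having received at least one dose of study drug" for safety.

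The first response scan comes "after induction (after fourth dose of induction rituximab and prior to starting consolidation" (5.1, Table 5, footnote 2). The same footnote calls for an End of Treatment scan 3 to 4 weeks after the last dose.

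Section 6.2.2.2 foresees "Patients with a global deterioration of health status requiring discontinuation of treatment without objective evidence of disease progression" and gives them a label of their own, but no place in the ORR.

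Section 10.1.2 gives the hypotheses, the error rates and a futility rule applied "among the first 15 patients enrolled, the trial will be stopped". It names no analysis set for the ORR and no final cut-off. Section 7.5 bases the interim rule on patients treated, where 10.1.2 says enrolled.

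Under 4.9, a Phase II patient who is never treated, or "who completes fewer than two total cycles of therapy and is withdrawn for any reason except POD or toxicity, shall be replaced". It does not say whether a replaced patient who was treated stays in the denominator.

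**The concern.** Being in the response set depends on what happens after treatment starts. Three kinds of treated patient can drop out of it: one who stops for toxicity after one or two brentuximab doses, one who dies before a scan, and one who deteriorates without documented progression. Deaths and deteriorations are treatment failures in any ordinary sense, so removing them raises the response rate that is compared with a fixed 50%.

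Section 4.9 does not settle the matter. Toxicity stops are not replaced, which might mean that they stay among the 24 as failures, but 6.2.1.1 makes them non-evaluable. A patient withdrawn for deterioration before two cycles is replaced if the withdrawal is classed as neither progression nor toxicity, and the plan does not say whether that patient still counts.

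The choice of denominator is therefore open until the data are seen, in a trial small enough for one patient to matter.

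**Working it through.** **Inputs from the documents.** Null 0.50, alternative 0.70, alpha below 0.05, beta below 0.20, stop at 8 or fewer responses in the first 15, expected sample size 24 (10.1.2); 24 patients to be enrolled (10.2).

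**Assumptions, not in the documents.** Share left out s = 5% or 10%. Response rate among those left out q = 0, 0.25 or 0.50. A final rule of at least 17 responses in 24.

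**1. The plan's own figure.** An exact search for the optimal two-stage design gives 8/15 then 26/43. At p=0.5 the probability of early stopping is 0.696, so the expected N is 15 + (1 − 0.696) × 28 = 23.5, which rounds up to the stated 24. Alpha is 0.0499 and power 0.804. So 24 matches the expected N of a design whose maximum is 43. The 17/24 rule below is the smallest cut-off that keeps alpha under 0.05 at 24 patients with the 8/15 look (alpha 0.032, power 0.56). It illustrates the issue and is not the plan's stated rule.

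**2. Bias in the ORR.** If the true ORR in all treated patients is 0.5, the ORR in the evaluable set is (0.5 − s × q) / (1 − s).

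| q | s = 5% | s = 10% |
|---|---|---|
| 0 | 0.500/0.95 = 52.6% | 0.500/0.90 = 55.6% |
| 0.25 | 0.4875/0.95 = 51.3% | 0.475/0.90 = 52.8% |
| 0.50 | 0.475/0.95 = 50.0% | 0.450/0.90 = 50.0% |

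**3. Type I error under the assumed 17/24 rule with the 8/15 look** (0.032 when nobody is left out).

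| Handling | q | s = 5% | s = 10% |
|---|---|---|---|
| No replacement, cut-off fixed at 17 | 0 | 0.032 | 0.032 |
| No replacement, cut-off fixed at 17 | 0.25 | 0.024 | 0.018 |
| No replacement, cut-off re-derived* | 0 | 0.058 | 0.084 |
| No replacement, cut-off re-derived* | 0.25 | 0.045 | 0.051 |
| No replacement, cut-off re-derived* | 0.50 | 0.034 | 0.030 |

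*Smallest count with exact one-sided p ≤ 0.05 on the evaluable n.

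With a fixed cut-off and no replacement, only the estimate is inflated. The error rate rises only if the cut-off shrinks with the denominator and those left out respond less often than the rest.

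**4. One patient.** Exact one-sided tails at p=0.5, single-stage test assumed: P(X ≥ 16 | 24) = 0.076 and P(X ≥ 16 | 23) = 0.047. The ORR moves from 66.7% to 69.6%. The chance that at least one of 24 patients is left out is 1 − (1 − s)^24: 38%, 71% or 92% at s = 2%, 5% or 10%.

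**5. What the End of Treatment scan can recover.** It can supply the repeat assessment for a patient who had three doses but missed the post-Induction scan. For a patient with one or two doses the three-dose condition still fails, unless the scan shows progression before the end of cycle 1. If both drugs stop after the day 8 dose, the scan falls due on day 8 + 21 = 29 to day 8 + 28 = 36, which is after a 28-day Induction cycle.

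**The case against.** **Safeguards.** Besides the End of Treatment scan, 4.1.5 asks for imaging when progression is suspected, 6.2.2.2 asks sites to try to document progression even after treatment stops, and 6.2.1.1 takes early objective progression back in. These stand and make the excluded group smaller. They do not reach a patient who dies unscanned, or one who stops before three doses without progression.

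**Direction.** Not everyone left out need be a failure. Table 4 in 4.3 lets rituximab continue when toxicity is attributed to brentuximab vedotin, so a patient with one or two brentuximab doses may still respond. Section 10.1.2 itself puts the ORR with rituximab, with or without chemotherapy, at about 50%, and at that rate among those left out the bias is zero. This also stands: the upward direction is plausible for deaths and deteriorations but not shown for toxicity stops.

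**Type I error.** A reader might infer that the plan's error rate roughly doubles or triples. If everyone left out were replaced, the 17/24 rule would give 0.055 or 0.094 at q=0. The documents do not support that reading, because 4.9 does not replace toxicity stops and no final cut-off is stated.

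**Share left out.** A reader might also carry over the 21% who stopped for adverse reactions in 1.2.1.1. That figure covers whole monotherapy courses with medians of 27 and 24 weeks, whereas three weekly doses take about three weeks. The share here is probably much lower.

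**Prespecification.** A response-evaluable set is a legitimate explicit choice. But 10.1.2 does not adopt it for the primary test, and its interim rule counts enrolled patients.

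**Conclusion.** The concern holds in a conditional form. Section 6.2.1.1 states a rule that leaves some treated patients out of the response analysis, and nothing in 10.1.2, 7.5, 4.9 or 6.2.2.2 overrides it or says how they count.

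If those left out respond less often than the rest, the ORR is too high: by 1.3 to 5.6 percentage points at a true 50%, for 5% to 10% left out and a response rate of 0 to 25% among them. It is unbiased if they would respond at 50%. The excluded share is assumed. The documents also do not say whether the 50% benchmark was itself calculated on treated or on evaluable patients.

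Type I inflation cannot be claimed as a property of this protocol. It ranges from none to 0.084 over the no-replacement scenarios under an assumed cut-off. What can be said firmly is that the denominator is undefined where one patient can decide the result. It should be corrected before the analysis.

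**What to change.** In 6.2.1.1 and 10.1.2, define the primary response set as all Phase II patients with measurable baseline disease who receive at least one dose of study drug. State that a patient without a documented response at the post-Induction or post-Consolidation assessment, for any reason, counts as a non-responder. Use this set for the first 15 patients in both 10.1.2 and 7.5 and for the final analysis, and state the cut-off for the actual N. Add to 4.9 that a replaced patient who received study drug stays in the primary denominator. Keep the three-dose set as a sensitivity analysis.

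The cost is protocol wording and one extra analysis; no new data are needed. N may slightly exceed 24. The reported ORR, and with it the chance of success, may be somewhat lower. If 70% was meant for evaluable patients and 5% or 10% of treated patients are early failures, the ORR in the new set is 0.70 × 0.95 = 66.5% or 0.70 × 0.90 = 63.0%. The chance of success under the assumed 17/24 rule then falls from 0.56 to 0.41 or 0.28.

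Two conflicts need separate reconciliation: whether stable disease or marrow-only resolution counts as response (2.3.2 against 7.5 and 9.2.2), and whether the futility bound is 8/15 (10.1.2) or 4/15 (7.5).

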6.2.1.2 Evaluable for Survival

All patients who have had at least one dose of study treatment will be evaluable for PFS and OS.

6.2.1.3 Evaluable for Other Endpoints

- Time to cytotoxic chemotherapy will be evaluated in all patients who receive at least one dose of study treatment.
- Effect on EBV markers will be evaluated in all patients who receive at least one dose of study treatment and have an evaluable TMA collected at baseline.
- Rates of graft rejection will be evaluated in all patients who receive at least one dose of study treatment

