1.4 Correlative Studies

In addition to the overall goals of this study, we plan to assess whether and to what extent immunohistochemical biomarkers might correlate with efficacy and outcome in this

population. We will also plan to collect and store whole blood samples (phase II patients only) for future, unspecified use.

- 1.4.1 A tissue microarray (TMA) of paraffin-embedded lymphoid tissue biopsies of all patients (enrolled in both Phase I and Phase II) will be created and analyzed by [name], hematopathologist and sub-investigator. This TMA will quantify expression of CD30, markers of EBV proliferation, and other markers known to be of prognostic significance in lymphoma (eg, Ki-67 and C-Myc), in order to determine how such markers correlate with clinical outcome.

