2.2 Secondary Objectives (Phase II only)

- 2.2.1 To further evaluate the frequency and severity of toxicity.
- 2.2.2 To further evaluate the clinical efficacy of the combination of brentuximab vedotin and rituximab, as measured by PFS and OS at one year after the end of treatment.
- 2.2.3 To evaluate the best response to therapy.
- 2.2.4 To determine the effects of the combination of brentuximab vedotin and rituximab on markers of EBV activation and proliferation.
- 2.2.4 Further evaluate efficacy as measured by time to cytotoxic chemotherapy.
- 2.2.5 Further evaluate efficacy as measured by observed rates of graft rejection.

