2.3 Primary Endpoints

- 2.3.1 The primary endpoint for phase I, dose-limiting toxicity (DLT) will be defined as the occurrence of toxicity as detailed in section 4.2 (using CTCAE v 4.03), experienced during the first 3 weeks of study treatment. The MTD, which constitutes the RP2D, will be defined as described in Section 11 (Study Design).
- 2.3.2 The primary endpoint for phase II, response after induction or induction/consolidation, will be defined as the detection of SD, PR, or CR by CT or PET/CT, and/or resolution of marrow-only involvement. CR and PR will each be assessed according to the Revised Response Criteria for Malignant Lymphoma. Assessments will be performed after induction and/or consolidation treatment (if applicable).

2.4 Secondary Endpoints:

- 2.4.1 Adverse events will be defined as those included in CTCAE v 4.03. The occurrence and severity of each will be recorded.
- 2.4.2 PFS will be defined as the time elapsed between treatment initiation and tumor progression or death from any cause (whichever occurs first), with censoring of patients who are lost to follow-up. OS will be defined as freedom from death by any cause.
- 2.4.3 Best response will be assessed by CT or PET/CT according to the Revised Response Criteria for Malignant Lymphoma after induction and/or consolidation (if applicable) and every 12 weeks during maintenance treatment.
- 2.4.4 EBV activation and proliferation will be measured by viral loads as measured at time of enrollment and monthly thereafter in all enrolled patients, until completion of study therapy.
- 2.4.5 Time to initiation of cytotoxic chemotherapy will be defined as the time elapsed between treatment initiation, and time of first non-targeted cytotoxic chemotherapy.
- 2.4.6 Graft rejection will be defined as any of the following: documentation of new or progressive rejection by tissue biopsy of the graft; re-transplantation due to graft rejection; clinical diagnosis of new or progressive graft rejection, since start of treatment on protocol, as given by the patient's transplant physician. Escalation of intensity of immunosuppression will not, by itself, be considered evidence of graft rejection. (Note: patients with clinically active graft rejection will not be excluded from trial enrollment, but will not be considered to have treatment-emergent graft rejection unless progression of rejection is documented.)

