2.6 Exploratory Endpoints

Levels of CD30 expression, EBV proliferation, and tumor proliferation (ie, Ki-67), all obtained from TMAs performed on pre-treatment tissue samples, will be correlated with ORR, as well as with EFS at one year. Quantitative serum EBV levels will be monitored for the duration of treatment, and change in levels correlated with ORR, duration of response, and progression of disease.

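### Section 6.2.1.3 requires an evaluable baseline tissue microarray for an EBV endpoint that section 2.4.4 defines by viral load in all enrolled patients

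*Combined protocol and SAP*

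**What the plan says.** **Objective.** The EBV item among the phase II secondary objectives (the first of two numbered 2.2.4) reads "To determine the effects of the combination of brentuximab vedotin and rituximab on markers of EBV activation and proliferation".

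**Endpoint.** Section 2.4.4 says how this is measured: "EBV activation and proliferation will be measured by viral loads as measured at time of enrollment and monthly thereafter in all enrolled patients", until study therapy is complete. Table 5 carries the measurement on its own row, "Serum EBV viral load", separate from the TMA row.

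**Analysis set.** Section 6.2.1.3 states: "Effect on EBV markers will be evaluated in all patients who receive at least one dose of study treatment and have an evaluable TMA". The condition in full is that they "have an evaluable TMA collected at baseline". The other two items in that list, time to cytotoxic chemotherapy and graft rejection, need only one dose of study treatment.

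**The TMA.** Section 1.4.1 describes its content: "This TMA will quantify expression of CD30, markers of EBV proliferation", along with other prognostic markers. Section 2.6 says that the CD30, EBV and tumor proliferation measures are "all obtained from TMAs performed on pre-treatment tissue samples". Table 5, footnote 5 adds: "Procurement of tissue and completion of TMA may be done prior to or upon enrollment, but are not required for registration/eligibility purposes". Sections 1.4.1 and 9.3 plan a TMA and tissue collection for all enrolled patients.

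**The concern.** The endpoint is a change over time in a blood measurement. The condition for entering its analysis is a tissue assay made once, before treatment. A patient can have every planned viral load and still fail the condition, and the plan gives no reason why that patient should not count.

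Two things are at stake. One is precision: phase II plans 24 patients, so each one removed matters a little. The other is clarity about the denominator. One analyst could follow 2.4.4 and report all treated patients with viral loads. Another could follow 6.2.1.3 and report only those with an evaluable TMA. Both could cite the plan, and the choice could be made after the data are seen.

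**Working it through.** The plan gives no figure for the EBV endpoint or its analysis set, so there is nothing to reproduce. The check is a comparison of the sections, followed by an illustration of size.

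**Step 1: is the TMA needed for the endpoint?**

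| | Viral load (2.4.4, Table 5) | TMA (1.4.1, 2.6, Table 5) |
|---|---|---|
| Material | Blood | Tissue |
| Timing | Enrollment, then repeatedly on treatment | Pre-treatment only |
| Can it show a change on treatment? | Yes | No, there is one time point |
| Planned in | All enrolled patients | All enrolled patients, but not required for registration |

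A change in viral load uses only the first column. Section 9.2.4 bears this out: it analyses serum EBV as detectable or undetectable and makes no use of the TMA.

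**Step 2: can a treated patient lack an evaluable TMA?** Yes. Footnote 5 lets a patient register without one, and collected tissue may still not give an evaluable array. No rate is stated.

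**Step 3: does the condition select EBV-positive disease?** No. It asks for an evaluable TMA, not an EBV-positive one. A patient with an evaluable but EBV-negative array stays in. A patient with a high viral load and no array drops out.

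**Step 4: size, as an illustration.** Inputs: N = 24 (section 10.2), and an assumed share without an evaluable TMA of 0 to 25%, which is not in the documents. The approximate 95% half-width for a proportion near 50% is 1.96 × √(0.25/n).

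- 0% missing, n = 24: 1.96 × √(0.25/24) = 0.200, or 20 points.
- 25% missing, n = 24 × 0.75 = 18: 1.96 × √(0.25/18) = 0.231, or 23 points.

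Exact (Clopper-Pearson) intervals agree. The full width is 0.418 for 12/24. With 10% missing (11/22) it is 0.436, and with 20% missing (9/19) it is 0.467. Beyond the assumed range, at 30% missing (8/17), it is 0.492.

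Clearance of EBV can be seen only in patients detectable at baseline, so its denominator may be smaller than 24 to begin with. Under the approximate formula, losing a quarter of any denominator widens the half-width by the same factor, √(1/0.75) = 1.155.

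**The case against.** **The bullet may be meant for tissue markers.** This is the strongest reply. In section 9, EBV markers means EBER, LMP-1 and EBNA-2 in tissue, and viral load is called the serum level of EBV. The Amendment 7 entry in the change log says that evaluability descriptions were added for exploratory objectives, among others. On that reading the TMA condition is right. The ambiguity is real, but the reading does not clear the text. All three items in 6.2.1.3 match secondary objectives in 2.2, and a single pre-treatment array cannot show an effect of treatment. If the bullet did cover tissue markers only, the viral-load endpoint would have no evaluability rule, and the section would still need an edit.

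**The two sections can both be obeyed.** In 2.4.4, the phrase about all enrolled patients governs measurement, not analysis. That is correct: the defect is an unexplained restriction of the analysis set, and not a logical impossibility.

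**Tissue is planned for everyone.** Histological confirmation is an entry criterion (3.1.1) and a pathology report is uploaded before registration (11.4.3), so diagnostic tissue should exist for each patient. Footnote 5 speaks only to what must be in hand at registration. This stands, and it means the loss may be near zero.

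**The endpoint carries no test.** It is secondary, with no hypothesis, power or decision rule. This also stands and limits the weight of the point.

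**Requiring a later viral load selects patients too.** This is true. Early withdrawals and deaths may have no later value, and they need not resemble the rest. The fix therefore has to report them.

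**Conclusion.** The point holds in a limited form. As written, 6.2.1.3 would exclude treated patients with valid viral loads from the analysis of the endpoint defined in 2.4.4, on a condition which that endpoint does not need. At an assumed loss of 0 to 25% of 24 patients, the half-width grows by about 3 points at most. The primary endpoint is untouched.

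A reader might infer more than the documents support:

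- *That the TMA has nothing to do with EBV.* It measures tissue EBV markers. The supportable statement is only that viral load does not depend on it.
- *That missing arrays are to be expected.* They are possible; the plan is to have one for all patients.
- *That the exclusion biases the result, for instance because small or urgent biopsies yield no array.* The documents do not say why an array would be missing and do not link its absence to viral-load change. Bias cannot be ruled out, but neither its direction nor its size can be shown.
- *That the viral-load data are thrown away.* They are still collected in all enrolled patients, and sections 2.6 and 9.2.4 use serum EBV without a TMA condition. Only the analysis governed by 6.2.1.3 is restricted.

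**What to change.** Rewrite the EBV bullet in 6.2.1.3 as two rules.

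1. **Viral load (2.2.4, 2.4.4).** Evaluate all patients with at least one dose of study treatment and a baseline viral load, with no TMA condition. Analyse change in those with at least one later value, and report how many have none and why. Report clearance among those detectable at baseline.
2. **Tissue markers (2.5.1, 2.5.2, 9.2.2).** Keep the requirement for an evaluable baseline TMA.

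This is a short text change that needs no new data, visits or patients. The small downside is that the viral-load and tissue-marker analyses may have different denominators, so each should be reported with its own n.
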